2.2.2 Efficacy Analysis Sets

2.2.2.2 Per Protocol Set (PP)

2.2.2.3 Intent-To-Treat non-infected (ITT-ni) Set

2.2.4 Pharmacokinetics Analysis Set

2.2.5 Pharmacodynamics Analysis Set

Summary of changes: Baseline resistance categories were defined based on influenza polymerase basic protein 2 genotype and phenotype. General re-formatting to assist readability of the section. The subgroups influenza season, study period (pre- and post-interim) and COVID-19 impacted (yes/no) are added.

2.3 Definition of Subgroups

Summary of changes: Detailing the definition of baseline ECG measurement was added. The baseline HRS is clarified. The last study visits for vital signs, NEWS2, ECG and central laboratory parameters are also defined.

2.5 Baseline and Endpoint

Summary of changes: A new section (2.6) was added to describe details of the analysis to support marketing authorization approval by FDA and EMA where a subset of patients is used with oseltamivir use as part of their SOC treatment and to include text to allow for potential analyses for other regions or countries

2.6 Other Definitions

Summary of changes: The number of subjects impacted by COVID-19 are added in the disposition table per analysis set. The table showing the number of subjects that discontinued is extended to show the number of subjects that discontinued due to COVID-19. Missed visits or changed visits due to COVID will also be presented. A listing showing the exposure to study drug for subjects impacted by COVID-19 is added. Major and minor protocol deviations related to COVID-19 are included. Concomitant therapy that was taken for COVID-19 infection are presented in an additional table.

4 SUBJECT INFORMATION

4.1 Demographics and Baseline Characteristics

4.2 Disposition Information

4.4 Extent of Exposure

4.5 Protocol Deviations

4.6 Prior and Concomitant Medications

Summary of changes: A new section (5.1.3) was added to describe how the actual values of the stratification factors are derived.

5.1.3 Stratification Factors

Summary of changes: The text describing the estimand is updated to align with the ICH E9 addendum guidance and to include MI methods for missing HRS values due to COVID-19 and not due to COVID-19

5.2.2 Estimand

Summary of changes: the multiple imputation methods are applied on the missing HRS values at day 6 due to COVID-19 and to missing HRS values on day 6 not due to COVID-19 in case the prevalence is more than $> 5\%$. A table is added to show the number (%) missing HRS values on day 6 by reason of missing.

5.2.3 Analysis Methods

Summary of changes: The fundamental hospital recovery scale, reflecting the actual location/situation of the subject evaluated daily from Day 2 to Day 14 is added. Time to NEWS2 ≤ 2 , time to clinical improvement, time to clinical failure and incidence of mortality per day are

added secondary endpoints. Re-hospitalizations are defined at the description of time to hospital discharge.

5.3.1.1 Clinical Outcome

Summary of changes: Adverse events leading to study discontinuation, AEs, serious AEs and non-serious AEs related to COVID-19 were added to the list for the adverse events summary table. The definition of a treatment emergent AE was detailed. A table of influenza related complications as assessed by the investigator was added. Tables that show AEs related to COVID-19 infection, SAEs related to COVID-19 infection, AEs related to COVID-19 infection leading to death and a listing showing the AEs related to COVID-19 infection are added.

7.1.1 Definitions

7.1.2 Analysis Methods

Summary of changes: The change from baseline in EQ-5D VAS is categorized in two ways providing two additional endpoints.

5.3.1.3 Other Patient Reported Outcome

Summary of changes: A bootstrapping method for calculating the median time to event with 95% confidence interval from the accelerated failure time model was added.

5.3.2 Analysis Methods

Summary of changes: Additional details regarding number of loose stools per day and stool consistency will be collected for subjects who report diarrhea adverse events. A confirmed diarrhea event is defined and the analysis of these events is described.

7.1.1 Definitions

7.1.2 Analysis Methods

Summary of changes: The use and definition of NEWS2 is explained and added.

NEWS2 will be used in the analyses.

7.6 NEW Score

Summary of changes: A new section was added to describe the analysis of the pharmacokinetic parameters and to explore their relationships with efficacy and safety.

9 Pharmacokinetics/Pharmacodynamics

9.1 Pharmacokinetics

9.2 Pharmacokinetic/Pharmacodynamic Relationships

Summary of changes: the anticipated events table has been corrected for a typo and to include an additional MedDRA preferred term for diabetic complications

[Attachment 1](#)

ABBREVIATIONS

ACVPU	Alert, new confusion, voice, pain, unresponsive
AE	adverse event
AFT	accelerated failure time
ATC	Anatomical Therapeutic Chemical
AUC	area under the curve
AUC _{12h}	area under the plasma concentration-time curve from time 0 to 12 hours
bid	bis in die; twice daily
BMI	body mass index
CI	confidence interval
C _{max}	maximum plasma concentration
COPD	Chronic Obstructive Pulmonary Disease
CTP	clinical trial protocol
C _{trough}	Plasma concentration just prior to the beginning or at the end of a dosing interval
CV	coefficient of variation
DBP	diastolic blood pressure
DMC	Data Monitoring Committee
DPS	Data Presentation Specifications
EC ₅₀	50% effective concentration
ECG	electrocardiogram
eCRF	electronic case report form
EMA	European Medicines Agency
ePRO	Electronic Patient-reported outcome (Device used for recording of patient-reported outcomes)
EQ-5D	European Quality of Life 5 Dimensions
FDA	Food and Drug Administration
GMR	geometric mean ratio
HRS	Hospital recovery scale
IC ₅₀	50% inhibitory concentration
ICF	informed consent form
ICH	International Conference on Harmonization
ICU	Intensive Care Unit
IDMC	Independent Data Monitoring Committee
ITT	Intent-To-Treat
ITT-i	Intent-To-Treat infected
ITT-ni	Intent-To-Treat non-infected
IWRS	Interactive web response system
LOD	limit of detection
LOQ	Limit of quantification
MedDRA	Medical Dictionary for Regulatory Activities
MT	Mid-turbinate
NAI	neuraminidase inhibitor
NEWS	National early warning score
NEWS2	National early warning score 2
OST	oseltamivir
PA	Polymerase acidic protein
PB2 (1)	polymerase basic protein 2 (1)
PD	pharmacodynamic(s)
PGIC	Patient Global Impression of Change
PGIS	Patient Global Impression of Severity
PK	pharmacokinetic(s)
PP	Per Protocol
PT	preferred term
qRT-PCR	quantitative real time polymerase chain reaction
SDTM	Subject Data Tabulation Model
SAE	serious adverse event
SAP	statistical analysis plan

SBP	systolic blood pressure
SI	international system
SOC	standard of care
SSG	Statistical support group
TEAE	Treatment Emergent Adverse Events
T _{max}	Time to reach C _{max}
VAS	Visual analogue scale

1. INTRODUCTION

This statistical analysis plan (SAP) contains definitions of analysis sets, derived variables and statistical methods for the analysis of efficacy and safety of the investigational compound pimodivir (JNJ-63623872). Separate documents for mock shells and table of contents for TFLs (DPS) are also produced. The SAP is to be interpreted in conjunction with the protocol.

Pimodivir (formerly known as VX-787 and JNJ-63623872) is a non-nucleotide inhibitor of the polymerase basic protein 2 (PB2) subunit of the influenza A virus polymerase complex and is currently in Phase 3 development as treatment for influenza A infection.

1.1. Trial Objectives

Primary Objective

The primary objective is to evaluate superiority of pimodivir in combination with standard-of-care (SOC) treatment compared to placebo in combination with SOC treatment on Day 6, with respect to the clinical outcome on the hospital recovery scale.

Secondary Objectives

The secondary objectives are:

- To investigate the safety and tolerability of pimodivir in combination with SOC treatment compared to placebo in combination with SOC treatment.
- To evaluate superiority with respect to the time from start of study drug to hospital discharge in subjects treated with pimodivir in combination with SOC treatment compared to placebo in combination with SOC treatment.
- To evaluate superiority with respect to the time from intensive care unit (ICU) admission to ICU discharge in subjects treated with pimodivir in combination with SOC treatment compared to placebo in combination with SOC treatment.
- To evaluate superiority with respect to the time from start to end of mechanical ventilation in subjects treated with pimodivir in combination with SOC treatment compared to placebo in combination with SOC treatment.
- To evaluate superiority of pimodivir in combination with SOC treatment compared to placebo in combination with SOC treatment each separated day from Days 2 to 14 (excluding the primary time point), with respect to the clinical outcome on the hospital recovery scale.
- To evaluate superiority with respect to the time to return to daily activities in subjects treated with pimodivir in combination with SOC treatment compared to placebo in combination with SOC treatment.
- To evaluate superiority with respect to the incidence of complications associated with influenza after the start of study treatment in subjects treated with pimodivir in combination with SOC treatment compared to placebo in combination with SOC treatment.
- To investigate all-cause mortality in the pimodivir in combination with SOC treatment arm, compared to the placebo in combination with SOC treatment arm.

- To investigate the incidence and duration of antibiotic treatment in the pimodivir in combination with SOC treatment arm, compared to the placebo in combination with SOC treatment arm.
- To investigate the number (proportion) of subjects needing extended treatment in the pimodivir in combination with SOC treatment arm, compared to the placebo in combination with SOC treatment arm.
- To investigate the number (proportion) of subjects requiring re-hospitalization in the pimodivir in combination with SOC treatment arm, compared to the placebo in combination with SOC treatment arm.
- To investigate the number (proportion) of subjects not hospitalized at Day 6 in the pimodivir in combination with SOC treatment arm, compared to the placebo in combination with SOC treatment arm.
- To investigate the time to clinical response in the pimodivir in combination with SOC treatment arm, compared to the placebo in combination with SOC treatment arm.
- To investigate the time to improvement of respiratory status in the pimodivir in combination with SOC treatment arm, compared to the placebo in combination with SOC treatment arm.
- To assess the pharmacokinetics (PK) of pimodivir and to explore the PK/pharmacodynamics (PD) relationships of pimodivir for efficacy and safety.
- To investigate the acceptability (taste and swallowability) of the pimodivir formulation in adolescents.
- To evaluate superiority with respect to the following influenza A viral parameters in the pimodivir treatment arm compared to the control arm by qRT-PCR and viral culture:
 - Time to viral negativity.
 - Viral load over time.
- To investigate the emergence of viral resistance against pimodivir detected by genotyping and/or phenotyping.

1.2. Trial Design

This is a Phase 3 randomized, double-blind, placebo-controlled, multicenter study to evaluate the efficacy and safety of pimodivir in combination with SOC treatment vs placebo in combination with SOC treatment in adolescent (13 to 17 years), adult (18 to 65 years), and elderly (>65 to ≤85 years) hospitalized subjects with influenza A infection. A target of 600 hospitalized influenza A-infected subjects will be randomly enrolled in this study with 300 subjects planned per treatment arm. The aim is to enroll a minimum of 60 adolescent subjects in this study in selected countries and study sites consistent with local regulations. The randomization will be stratified for screening NEWS2 (4-5 or >5) (NEWS is changed to NEWS2 per CTP amendment 2), type of baseline SOC (including or not including influenza antiviral treatment), and time since onset of influenza symptoms (first administration of study drug within 72 hours or between 72 and 96 hours since onset of influenza symptoms). The study population should consist of at least 75% of subjects

(75% of the total planned sample size of 600 subjects) with first administration of study drug ≤ 72 hours since onset of influenza symptoms.

Subjects who meet all eligibility criteria will be randomized in a 1:1 ratio to receive 1 of the following treatments.

- Treatment Arm 1: pimodivir 600 mg bid for 5 days + SOC treatment*
- Treatment Arm 2: pimodivir placebo bid for 5 days + SOC treatment*

*SOC treatment is determined by the investigator based on local practice, and may include influenza antivirals and/or supportive care only. For further details see protocol Section 3.1.

1.3. Statistical Hypotheses for Trial Objectives

The primary endpoint is the hospital recovery scale as assessed on Day 6. The alternative hypothesis is that the outcome on the hospital recovery scale with pimodivir in combination with SOC treatment is statistically superior to treatment with placebo in combination with SOC treatment on Day 6 in hospitalized subjects with influenza A infection.

1.4. Sample Size Justification

The study will enroll 600 subjects between the ages of 13 and 85 years, inclusive. Subjects will be randomized 1:1 to one of the treatment arms.

The sample size is based on the primary endpoint of the hospital recovery scale at Day 6. Based on the proportional odds model and assuming a benefit of approximately 38% reduction of the common odds ratio, a total sample size of 600 subjects (randomized 1:1) is required to obtain a power of 90% [11]. Inclusion of stratification factors would provide some improvement on the derived power.

In the sample size calculation it is assumed that the distribution of subjects treated with placebo in combination with SOC treatment will be as follows on Day 6:

- Not hospitalized: 30%
- Non-ICU hospitalization, not requiring supplemental oxygen: 30%
- Non-ICU hospitalization, requiring supplemental oxygen: 25%
- Admitted to the ICU, not requiring invasive mechanical ventilation: 5%
- Requiring invasive mechanical ventilation: 5%
- Death: 5%

This sample size is robust to mild to moderate changes in this distribution.

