- The time since onset of influenza symptoms (first administration of study drug ≤ 72 hours or between 72 and 96 hours since onset of influenza symptoms) may influence the effectiveness of antiviral treatment. The earlier treatment can start, the more the antiviral medication can be effective by limiting the overall exposure to the virus. To limit study drug exposure to subjects with longer times since onset of influenza symptoms, the study will be set up such that the subgroup of subjects with first administration of study drug between 72 and 96 hours (72-to-96-hoursubgroup) since onset of influenza symptoms may be stopped during the study in case treatment appears not to be effective in this subgroup (futility) (see Section [11.12](#)).

Study Population

Patients hospitalized with influenza are more severely ill and are reported to shed virus longer compared to patients with uncomplicated disease with no need for hospitalization.¹⁸ In prospective studies, none of the commercially available agents have been shown to be efficacious in hospitalized patients, who have the greatest unmet medical need. However, they are used as de-facto SOC as recommended by the CDC, the European Center for Disease prevention and Control, and the World Health Organization (WHO) for this patient population.³

A number of prospective and retrospective studies of NAIs in severe influenza in the hospital setting have been conducted.¹¹ In retrospective studies, early treatment with the orally administered NAI OST had a favorable effect on outcome.¹⁸

Given the limitations of the currently available anti-influenza therapies, such as a short window for initiation of study treatment, concerns about drug resistance, and the lack of any demonstrated clinical benefit in the most fragile population of hospitalized patients, there is a clear high unmet medical need for better influenza therapies.

Dose Regimen Selection

The dose of pimodivir (600 mg bid for 5 days) was selected based on efficacy and PK/PD modeling data, as well as safety and viral resistance data from the completed Phase 2 studies (FLZ2001 and FLZ2002).

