11.12. Interim Analysis

All interim analyses will be performed by an independent Statistical Support Group (SSG) and will be reviewed by the Independent Data Monitoring Committee (IDMC; see Section 11.13). Only the IDMC and the SSG will be unblinded to the data. The IDMC will provide recommendations to a Sponsor Committee.

An interim analysis will be implemented to assess lack of efficacy in the subgroup with time since onset of influenza symptoms between 72 and 96 hours.

- In case lack of efficacy is concluded for the subgroup with time since onset of influenza symptoms between 72 and 96 hours:
 - Enrollment in this subgroup will be stopped
 - Sample size re-estimation will be performed based on the subgroup with time since onset of influenza symptoms ≤ 72 hours and consequently, the sample size of this subgroup may be increased. The maximum number of subjects that may be enrolled in this subgroup will be approximately 900.
 - Futility will be assessed in the subgroup with time since onset of influenza symptoms ≤ 72 hours based on re-estimated sample size.
 - At the final analysis, hypotheses will be evaluated in the subgroup with time since onset of influenza symptoms ≤ 72 hours.
- In case no lack of efficacy is concluded for the subgroup with time since onset of influenza symptoms between 72 and 96 hours:
 - The subgroup with time since onset of influenza symptoms between 72 and 96 hours will be continued in the study.
 - Sample size re-estimation will be performed based on all subjects. The sample size may be increased. The maximum total number of subjects that may be enrolled in the study will be approximately 900. The study population should consist of at least 75% of subjects with first administration of study drug ≤ 72 hours since onset of influenza symptoms.
 - Futility will be assessed in all subjects based on re-estimated sample size.
 - At the final analysis, hypotheses will be evaluated in all subjects.

Details on the statistical decision rules will be provided in a separate Modeling and Simulation Report. The interim analysis will be conducted at the end of the first influenza season when between 300 and 450 subjects have been enrolled or during the season when 450 subjects have been enrolled. Further details will be specified in the IDMC charter.

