3. INTERIM ANALYSIS AND DATA MONITORING COMMITTEE REVIEW

3.1. Interim Analyses

An interim analyses will be performed by an independent Statistical Support Group (SSG) and will be reviewed by the Independent Data Monitoring Committee (IDMC). Only the IDMC and the SSG will be unblinded to the data. The IDMC will provide recommendations to a Sponsor Committee.

An interim analysis will be implemented to assess lack of efficacy in the subgroup with time since onset of influenza symptoms between 72 and 96 hours.

- In case lack of efficacy is concluded for the subgroup with time since onset of influenza symptoms between 72 and 96 hours:
 - Enrollment in this subgroup will be stopped
 - Sample size re-estimation will be performed based on the subgroup with time since onset of influenza symptoms ≤ 72 hours and consequently, the sample size of this subgroup may be increased. The maximum number of subjects that may be enrolled in this subgroup will be approximately 900.
 - Futility will be assessed in the subgroup with time since onset of influenza symptoms ≤ 72 hours based on re-estimated sample size.
 - At the final analysis, hypotheses will be evaluated in the subgroup with time since onset of influenza symptoms ≤ 72 hours.
- In case no lack of efficacy is concluded for the subgroup with time since onset of influenza symptoms between 72 and 96 hours:
 - The subgroup with time since onset of influenza symptoms between 72 and 96 hours will be continued in the study.
 - Sample size re-estimation will be performed based on all subjects. The sample size may be increased. The maximum total number of subjects that may be enrolled in the study

will be approximately 900. The study population should consist of at least 75% of subjects with first administration of study drug ≤ 72 hours since onset of influenza symptoms.

- Futility will be assessed in all subjects based on re-estimated sample size.
- At the final analysis, hypotheses will be evaluated in all subjects.

Details on the statistical decision rules will be provided in the IDMC SAP. The interim analysis will be conducted at the end of the first influenza season when between 300 and 450 subjects have been enrolled or during the season when 450 subjects have been enrolled. Further details will be specified in the IDMC charter.

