- If the p-value is $> 5\%$, stop further testing of the secondary endpoints, and make a claim on “Hospital recovery scale at Day 6”, “Incidence in post-baseline complications”, “Time from start of study drug to hospital discharge”, “Time from ICU admission to ICU discharge”, and “Time to return to daily activities”.

Step 5: Test the sixth secondary endpoint (“Rate of re-hospitalization”)

- If the p-value is $\leq 5\%$, make a claim on “Hospital recovery scale at Day 6”, “Incidence in post-baseline complications”, “Time from start of study drug to hospital discharge”, “Time

from ICU admission to ICU discharge”, “Time to return to daily activities”, “Time from start to end of mechanical ventilation”, and “Rate of re-hospitalization”.

- If the p-value is >5%, make a claim on “Hospital recovery scale at Day 6”, “Incidence in post-baseline complications”, “Time from start of study drug to hospital discharge”, “Time from ICU admission to ICU discharge”, “Time to return to daily activities”, and “Time from start to end of mechanical ventilation”.

For the primary endpoint, the results from the proportional odds model will be used in the hypothesis testing. If the proportional odds assumption would not hold on the treatment effect, the p-value from the van Elteren test will be used. For the secondary endpoints time from start of study drug to hospital discharge, time from ICU admission to ICU discharge, time to return to daily activities, and time from start to end of mechanical ventilation, the results of the Gehan-Wilcoxon test will be used in the hypothesis testing. For incidence in post-baseline complications and rate of re-hospitalization the results of the logistic regression will be used. For all these evaluations p-value combination tests will be used, as described below.

The final analysis on the ITT-i set (to support FDA marketing approval) and the final analysis on the OST subset (to support marketing authorization approval in EMA) will be performed independently, using a 5% two-sided significance level for each.

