5.1.2. Statistical Methodology for Evaluation at the Final Analysis

All p-values below are one-sided p-values, to evaluate rejection of the null hypothesis that pimodivir is not better than placebo.

Scenario 1: The final analysis will be performed in the subgroup with time between onset of symptoms and start of treatment between 0 and 72 hours only. P-values for the final analysis will be based on 2 inverse-normal combination tests of p-values as outlined below.

Let:

- p = p-value (one-sided) from full study population of the pre-interim' category of the study period subgroup
- p_1 = p-value (one-sided) from subgroup with time between onset of symptoms and start treatment between 0 and 72 hours of the pre-interim' category of the study period subgroup
- p_2 = $2 * \min(p, p_1)$
- q_1 = p-value (one-sided), from subgroup with time between onset of symptoms and start treatment between 0 and 72 hours on the patients enrolled of the 'post-interim' category of the study period subgroup
- N_1 = actual sample size at interim i.e.:all randomized subjects analysis set (RAND) included in the IA
- N = 600, the initially planned study sample size
- w_1 = $\sqrt{N_1/N}$
- w_2 = $\sqrt{1-(N_1/N)}$
- $\phi^{-1}(x)$ = the inverse of the standard normal cumulative distribution function in x

Note: p_1 and q_1 are based on a subset of subjects with onset of symptoms and start treatment between 0 and 72 hours, and therefore this stratification factor is not included in the respective models.

The p-values resulting from the following 2 combination tests both should be below the pre-specified alpha (2.5% one-sided) to claim superiority in subgroup with time between onset of symptoms and start of treatment between 0 and 72 hours:

$$1-\phi(C(p_1, q_1)) \text{ where } C(p_1, q_1) = w_1 * \phi^{-1}(1-p_1) + w_2 * \phi^{-1}(1-q_1)$$

$$1-\phi(C(p_2, q_1)) \text{ where } C(p_2, q_1) = w_1 * \phi^{-1}(1-p_2) + w_2 * \phi^{-1}(1-q_1)$$

Scenario 2: The final analysis will be performed in the full study population. P-values for the final analysis will be based on 2 inverse-normal combination tests of p-values.

Let additionally:

- q = p-value from full study population on the patients enrolled of the 'post-interim' category of the study period subgroup

The p-values resulting from the following 2 combination tests both should be below the pre-specified alpha to claim superiority in the full study population:

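### The 90% power stated for N = 600 belongs to a single-stage test; under the SAP 5.1.2 rule that decides the claim, the same odds ratio gives about 85%

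*SAP*

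**What the plan says.** **Sample size.** SAP 1.4 states that "a total sample size of 600 subjects (randomized 1:1) is required to obtain a power of 90" per cent, and Protocol 11.3 says the same. Both base it on a proportional odds model, a reduction of about 38% in the common odds ratio, an assumed placebo distribution on Day 6 and a cited method for ordered categories. SAP 1.4 adds that "Inclusion of stratification factors would provide some improvement on the derived power", with no figure. Neither section mentions the interim analysis or a combination test.

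**Decision rule.** After naming the tests for the primary and six key secondary endpoints, SAP 5.1.1 says: "For all these evaluations p-value combination tests will be used, as described below". For the full population, SAP 5.1.2 says: "The p-values resulting from the following 2 combination tests both should be below the pre-specified alpha to claim superiority in the full study population". The two tests are C(p,q) and C(p2,q), with p2 = 2 × min(p, p1). Here p and p1 are the pre-interim one-sided p-values for all subjects and for those treated within 72 hours, and q is the post-interim p-value. The weights use N = 600 as the planned size. A parallel pair of tests applies if only the 72-hour subgroup is carried forward.

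**Interim.** If the full population continues, SAP 3.1 says: "Sample size re-estimation will be performed based on all subjects. The sample size may be increased", to a maximum of about 900. For the decision rules, SAP 3.1 says "Details on the statistical decision rules will be provided in the IDMC SAP", whereas Protocol 11.12 says "Details on the statistical decision rules will be provided in a separate Modeling and Simulation Report". Neither of those documents was available for this review.

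**The concern.** A reader of SAP 1.4 takes 90% to be the power of the planned primary test at 600 subjects. It is the power of a different and easier test. Doubling the smaller stage 1 p-value is a Bonferroni correction for the possible choice of population at the interim. It protects type I error but costs power, and a sample size formula for a single fixed test does not include that cost. At stake is the type II error the sponsor believes it has accepted at the stated size. It is the only power figure in either document.

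**Working it through.** **Inputs**
- Placebo distribution on Day 6, best to worst: 30/30/25/5/5/5% (SAP 1.4).
- Common odds ratio 0.62, from the 38% reduction; ln 0.62 = −0.478 (SAP 1.4).
- 1:1 allocation; two-sided 5%, that is 2.5% one-sided for each combination test (SAP 5.1.1, 5.1.2).
- Share treated within 72 hours: at least 75% (SAP 1.2); 75% used.
- Interim size N1: 300 to 450 (SAP 3.1).
- Weights w1 = √(N1/600), w2 = √(1 − N1/600) (SAP 5.1.2).

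**Step 1: reproduce the stated figure.** An odds ratio of 0.62 gives a treated distribution of 40.9/29.9/19.4/3.4/3.3/3.2%. With p̄ the mean of the two arms, 1 − Σp̄³ = 0.9175. The formula for ordered categories gives

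N = 12 × (1.960 + 1.282)² / (0.478² × 0.9175) = 601.4.

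The expected test statistic at 600 is 0.478 × √(600 × 0.9175 / 12) = 3.238, so power is Φ(3.238 − 1.960) = 89.9%. The stated 90% reproduces for a single-stage test.

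**Step 2: apply the SAP 5.1.2 rule to the same effect.** Stage-wise statistics were simulated as normal, with independent contributions from the two onset windows. The claim required both C(p,q) and C(p2,q) below 2.5% one-sided. C(p2,q) was counted as failed where p2 reached 1. Total N = 600, full population continuing, no sample size increase, no futility stop, no covariate gain.

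| Effect assumption | N1 = 300 | N1 = 375 | N1 = 450 |
|---|---|---|---|
| OR 0.62 in both windows | 85.1% | 85.2% | 85.2% |
| 72–96 h effect half the ≤72 h effect | 86.4% | 86.6% | 86.7% |
| No effect at 72–96 h | 88.2% | 88.5% | 88.7% |

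The last two rows keep the average log odds ratio at 0.478. Half effect: 0.478/0.875 = 0.546 (OR 0.58) within 72 hours and 0.273 (OR 0.76) later. No late effect: 0.478/0.75 = 0.637 (OR 0.53) and 0.

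**Step 3: locate the loss.** With equal effects, C(p,q) alone gives 89.9% and C(p2,q) alone 85.5–85.7%. The loss comes from the factor 2, not from splitting the trial into stages. A rough hand check at N1 = 300: the expected stage 1 statistic is 3.238 × √0.5 = 2.289, so p = 0.0110. Doubled, this is 0.0221, a statistic of 2.013. The combined statistic falls by (2.289 − 2.013) × √0.5 = 0.195, and Φ(3.238 − 0.195 − 1.960) = 86.0%. This is only approximate, because it uses expected values and one of the two tests.

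**Step 4: checks and sensitivity**
- Six-category multinomial data with a tie-corrected Wilcoxon statistic: single-stage 89.8%; rule with equal effects 84.8–85.1%.
- OR 0.615: 86.3–86.5% (single-stage 90.9%). OR 0.625: 83.8–84.0% (single-stage 89.0%).
- Share within 72 hours of 80–95%: 84.7–85.3%.
- Equal effects and larger N: about 710 subjects give 90%; 900 give 94.3–94.7%.
- Global null, full-population rule: about 1.5% one-sided.
- Only the 72-hour subgroup carried forward, equal effects, 600 in total with all post-interim enrolment within 72 hours: 82.6%, 81.7% and 80.6% for N1 = 300, 375 and 450.

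**The case against.** The strongest reply is that 600 with no increase is not the whole design. Re-estimation is planned whichever way the interim goes, up to about 900, and the rule then reaches 94–95% with equal effects. The power of the adaptive design depends on decision rules in documents not seen here, which may already report it. This stands as a limit: overall power cannot be computed from the protocol and SAP. It does not rescue the sentence in SAP 1.4, which states power at 600. An increase is optional, and neither sample size section refers to those documents.

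Second, equal effects in both windows is an assumption, and it gives the lowest of the three full-population cases. Protocol 3.2 says that time since onset "may influence the effectiveness of antiviral treatment". That is fair, and it is why a range is shown. Equal effects is nonetheless the plain reading of one common odds ratio, and the other two cases also fall short of 90%.

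Third, covariates help, and the SAP 5.2.3 model also includes baseline recovery scale category. The documents give no figure. If adjustment added 5%, 10% or 15% information (an assumption), the rule would give about 87%, 88.5% or 90%. But the same gain lifts the single-stage test: with 15%, 3.238 × √1.15 = 3.472 and Φ(3.472 − 1.960) = 93.5%. The gap narrows but remains, and SAP 1.4 presents any such gain as additional to the 90%.

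Fourth, one new figure would itself be incomplete, because SAP 5.1.2 has a second branch. That is correct, so the revised text should say that its figure applies when the full population continues.

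**Conclusion.** The concern holds. The 90% is computed correctly for a single-stage test, but that is not the test on which the claim rests. At N = 600 under SAP 5.1.2, power is about 85% with an odds ratio of 0.62 in both windows, and about 85–89% over the three effect patterns examined. All of these assume that the full population continues, with no sample size increase, futility stop or covariate gain. The result hardly depends on interim timing between 300 and 450 subjects. Neither calculation allows for missing Day 6 data or for randomized subjects excluded from the infected analysis set. This is a misstated planning figure, not an invalid analysis, and it does not show that the adaptive design as a whole is underpowered. It should be fixed.

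**What to change.** In SAP 1.4:
- State that 90% at N = 600 refers to a single-stage proportional odds test on all subjects.
- State that power at N = 600 under the SAP 5.1.2 full-population rule is about 85%, with an odds ratio of 0.62 in both onset windows, the full population continuing, no sample size increase, no futility stop and no covariate gain.
- Add that re-estimation up to about 900 and covariate adjustment may raise it, and cross-refer to the Modeling and Simulation Report and the IDMC SAP for the interim rules and for the branch restricted to 72 hours.

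Make the same change in Protocol 11.3 at the next amendment. Protocol 17.1 requires a formal amendment, and this point alone does not justify one. As optional tidying, cap p2 at 1 in SAP 5.1.2, with C(p2,q) failing at the cap; at an odds ratio of 0.62 this could affect at most 0.16% of trials.

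The cost is two or three sentences. No patients are added, and no test, threshold or enrolment rule changes.
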